### 8.1.2 Safety Analyses

The All-Patients-as-Treated population will be employed for safety analyses.

### 8.1.3 Power and Sample Size

Assuming that approximately 135 of the 150 enrolled subjects with recurrent and/or metastatic head and neck cancer will be evaluable for the primary efficacy analysis in the FAS population, the study has approximately 85% power to demonstrate that the ORR is  $>5\%$  with a type I error rate of 1.25% [redacted] Success for this hypothesis requires at least 14/135 responses.

Assuming that the prevalence of PD-L1 strong positive subjects with recurrent and/or metastatic head and neck cancer is 20%~30%, then among the 150 enrolled subjects approximately 30~45 PD-L1 strong positive subjects would be expected. The study has approximately 92% to 99% power to demonstrate that the ORR  $>5\%$  with a type I error rate of 1.25% if the [redacted] Success for this hypothesis requires at least 6 responses out of 30~39 PD-L1 strong positive subjects, and at least 7 responses out of 40~45 PD-L1 strong positive subjects.

### 8.1.4 Interim Analysis

No interim analyses are planned.

## 8.2 Statistical Analysis Plan

### 8.2.1 Responsibility for Analyses/In-House Blinding

The statistical analysis of the data obtained from this study will be the responsibility of the Clinical Biostatistics department of the Sponsor.

This trial is being conducted as an open-label non-randomized single-arm clinical trial, i.e., subjects, investigators, and Sponsor personnel will be aware of subject treatment assignments after each subject is enrolled and treatment is assigned. The study team at the Sponsor consisting of clinical, statistical, scientific programming and data management personnel, will be blinded to individual-level PD-L1 biomarker results until the time that a study report is written. While the study team is blinded to the PD-L1 patient-level biomarker results, an unblinded Sponsor statistician and Sponsor statistical programmer who will have access to the PD-L1 results for the purpose of data review and cleaning and will have no other responsibilities associated with the study. Summary reports of biomarker prevalence may be provided to the study team at the Sponsor by the IVRS vendor, the unblinded Sponsor statistician, and/or an unblinded external statistician.

The Clinical Biostatistics department will generate the allocation schedule(s) for study treatment assignment. Allocation will be implemented in an interactive voice response system (IVRS).

## 8.2.2 Hypotheses/Estimation

Objectives and hypotheses of the study are stated in Section 3.0.

## 8.2.3 Analysis Endpoints

Efficacy and safety endpoints that will be evaluated are listed below, followed by the descriptions of the derivations of selected endpoints.

### 8.2.3.1 Efficacy/Immunogenicity/Pharmacokinetics Endpoints

The primary efficacy endpoint is objective response rate (ORR), defined as the proportion of subjects in the analysis population who have complete response (CR) or partial response (PR) using RECIST 1.1 criteria at any time during the study. Response for the primary analyses will be determined by independent radiology review. ORR will be evaluated separately in all subjects and the subset of all PD-L1 strong positive subjects (defined as a PD-L1 tumor proportion score  $\geq 50\%$  by IHC).

Supportive analyses of ORR will be performed based on site assessments using RECIST 1.1.

ORR in all subjects with any PD-L1 positive will be a key secondary efficacy endpoint. PD-L1 positivity is defined as PD-L1 tumor proportion score  $>0\%$  by IHC. Other key secondary efficacy endpoints that will be evaluated in all subjects, all PD-L1 positive subjects, and all PD-L1 strong positive subjects include:

**Duration of Response:** defined as time from first RECIST 1.1 response to disease progression in subjects who achieve a PR or better

**ORR by modified RECIST 1.1:** defined as proportion of subjects with a CR or PR using modified RECIST 1.1 criteria as defined in Section 4.2.3.1.

**ORR among HPV positive subjects:** defined as the proportion of subjects with HPV positive tumor biopsy who achieve a CR or PR according to RECIST 1.1 criteria.

**Progression-free survival (PFS):** defined as the time from allocation to the first documented disease progression according to RECIST 1.1 or death due to any cause, whichever occurs first.

**Overall survival (OS):** defined as the time from allocation to death due to any cause.

Additional exploratory endpoints include PFS by modified RECIST 1.1 criteria and ORR/PFS/OS by exploratory candidate biomarkers.

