#### **4.1.3 Ongoing Clinical Trials**

Ongoing clinical trials of pembrolizumab are being conducted in advanced melanoma, non-small cell lung cancer, a number of advanced solid tumor indications and hematologic malignancies. For study details please refer to the IB.

Trials evaluating pembrolizumab in head and neck cancer have demonstrated clinical activity in patients with recurrent and/or metastatic disease. KEYNOTE 012 is a Phase Ib study of pembrolizumab in patients with human papillomavirus (HPV)-negative and HPV-positive head and neck cancer. This trial enrolled an initial 60 patient cohort with recurrent and/or metastatic squamous cell carcinoma of the head and neck for treatment with single agent pembrolizumab. Preliminary results from this cohort were reported at the Annual Meeting of the American Society of Clinical Oncology (ASCO) in 2014 [29], showing an overall response rate (confirmed and unconfirmed) of 19.6% (10 partial responses [PRs], 1 complete response [CR] out of 56 patients evaluable for response). An additional 16/56 patients (28.6%) experienced stable disease (SD), with 51% of patients experiencing some numerical decrease in tumor burden from baseline. Seventeen total patients with CR, PR, or SD remain on therapy at the time of the reporting for > 6 months. There were no new or unexpected toxicity signals in this patient cohort, with infrequent grade 3-4 drug-related (DR) adverse events (AEs).

Preliminary PD-L1 biomarker data from KEYNOTE 012 suggests that the response rate may be enhanced for patients with high PD-L1 IHC expression. Using a Youden-Index derived PD-L1 IHC cutpoint, the response rate (RR) in patients with high PD-L1 expression was 45.5% (5/11), compared to 11.4% (5/44) in low PD-L1 expression patients.

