#### **7.1.2.6.2 Tumor Imaging During Trial**

The first imaging assessment should be performed at 9 weeks (63 days  $\pm$  7 days) from the date of 1st dose. Subsequent imaging should be performed every 6 weeks (42 days  $\pm$  7 days), more frequently if clinically indicated. Subjects who remain on treatment for a year will have imaging performed every 9 weeks. Imaging should not be delayed for delays in cycle starts.

Per RECIST 1.1, response should be confirmed by a repeat radiographic assessment not less than 4 weeks from the date the response was first documented. The scan for confirmation of response may be performed at the earliest 4 weeks after the first indication of response, or at the next scheduled scan (6 weeks later), whichever is clinically indicated. Imaging should then return to the original schedule beginning with the next protocol-specified timepoint. Subjects who obtain a confirmation scan at 4 weeks do not need to undergo the next scheduled imaging assessment if it is due < 4 weeks later; imaging may resume at the subsequent scheduled timepoint. (e.g. If a subject obtains a scan at Week 13 to confirm a Week 9 response, they will not be required to complete the scheduled Week 15 scan. The next imaging would then occur at Week 21 as usual.)

Imaging should continue to be performed until radiographic disease progression, the start of new anti-cancer treatment, withdrawal of consent, death, or notification by the Sponsor, whichever occurs first. Disease progression may be confirmed at least 4 weeks after the first scan indicating progressive disease in clinically stable subjects. Subjects who have unconfirmed disease progression may continue on treatment until progression is confirmed provided they have met the conditions detailed in Section 7.1.2.6.3.

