#### 7.1.5.2.1 Second Course Phase (Retreatment Period)

Subjects who stop pembrolizumab (MK-3475) with SD or better may be eligible for up to one year of additional MK-3475 therapy if they progress after stopping study treatment. This retreatment is termed the Second Course Phase of this study and is only available if the study remains open and the subject meets the following conditions:

- Either
  - Stopped initial treatment with pembrolizumab (MK-3475) after attaining an investigator-determined confirmed CR according to RECIST 1.1
    - Was treated for at least 24 weeks with pembrolizumab (MK-3475) before discontinuing therapy AND
    - Received at least two treatments with pembrolizumab (MK-3475) beyond the date when the initial CR was declared

**OR**

- Had SD, PR or CR and stopped pembrolizumab (MK-3475) treatment after 24 months of study therapy for reasons other than disease progression or intolerance

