## 8.0 STATISTICAL ANALYSIS PLAN

This section outlines the statistical analysis strategy and procedures for the study. If, after the study has begun, but prior to obtaining PD-L1 positivity status, changes are made to primary and/or key secondary hypotheses, or the statistical methods related to those hypotheses, then the protocol will be amended (consistent with ICH Guideline E-9). Changes to exploratory or other non-confirmatory analyses made after the protocol has been finalized, along with an explanation as to when and why they occurred, will be listed in the Clinical Study Report (CSR) for the study. Post hoc exploratory analyses will be clearly identified in the CSR. No separate Statistical Analysis Plan (SAP) will be issued for this study.

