### **8.2.5.1 Statistical Methods for Efficacy Analyses**

For the primary efficacy endpoint independently reviewed ORR using RECIST 1.1, the point estimate, 97.5% confidence interval, and p-value for testing ORR is greater than the

historical control rate of 5% will be provided separately for all subjects and PD-L1 strong positive subjects using exact binomial distribution. Subjects in the primary analysis population (FAS) without response data will be counted as non-responder.

Efficacy for the key secondary endpoint of ORR among PD-L1 positive subjects, as well as other secondary analyses of ORR using modified RECIST 1.1 and ORR among subjects with HPV positive head and neck cancer will be evaluated in the same manner as in the primary analysis.

For the secondary analyses of response duration, PFS and OS, Kaplan-Meier (KM) curves and median estimates from the KM curves will be provided as appropriate. Subjects without efficacy evaluation data or without survival data will be censored at Day 1.

The primary analysis for each hypothesis will be conducted after all subjects have at least 6 months of follow-up. The final analysis of OS will occur when <5% of patients remain on study drug.

**Table 10** summarizes the key efficacy analyses.

Table 10      Analysis Strategy for Key Efficacy Variables

Endpoint	Statistical Method	Analysis Population	Missing data approach
ORR • RECIST 1.1, independent radiology review	Exact test of binomial parameter	FAS in all below populations: 

• all-comers

• PD-L1 strong positive*

• PD-L1 positive‡

	Subjects with missing data are considered non-responders
ORR • RECIST 1.1, independent radiology review • modified RECIST 1.1, independent radiology review • modified RECIST 1.1, investigator	Point estimate and exact binomial CI	FAS in all below populations: 

• all-comers

• PD-L1 strong positive*

• PD-L1 positive‡

• HPV positive

 APaT in all below populations: 

• all-comers

• PD-L1 strong positive

• PD-L1 any positive

• HPV positive

	Subjects with missing data are considered non-responders

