### 8.2.6 Multiplicity

The false positive rate for testing the primary efficacy hypotheses is controlled at 2.5% (1-sided) with 1.25% allocated to all subjects and 1.25% allocated to PD-L1 strong positive subjects. The key secondary efficacy hypothesis of ORR based on RECIST 1.1 assessed by independent radiology review in PD-L1 positive subjects will be tested at 1.25% (one-sided) if the primary efficacy hypothesis in PD-L1 strong positive subjects is rejected. If both the primary hypothesis for PD-L1 strong positive subjects and the key secondary efficacy hypothesis are rejected, the additional alpha level 1.25% will be allocated back to all subjects and the primary efficacy hypothesis for all subjects will be tested at 2.5% (Figure 2).

[figure not shown]

Figure 2 Multiplicity Strategy

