### 8.2.7 Sample Size and Power Calculations

Assuming that approximately 135 of the 150 enrolled subjects with recurrent and/or metastatic head and neck cancer will be evaluable for the primary efficacy analysis in the FAS population, the study has approximately 85% power to demonstrate that the ORR is  $>5\%$  with a type I error rate of 1.25% [28]. Success for this hypothesis requires at least 14/135 responses. The null ORR rate of 5% was determined based on a prior randomized trial of methotrexate therapy vs. gefinitib in a second line population in which an ORR of 4% was observed in the methotrexate arm [28].

The proportion of subjects who are PD-L1 strong positive among the 150 subjects enrolled is not known but is estimated to be approximately 20%~30%, then 150 subjects would be expected to provide 30~45 PD-L1 strong positive subjects with recurrent and/or metastatic head and neck cancer will be evaluable for the primary efficacy analysis in the FAS population. [Figure 3](#) shows the power curve ranging about 92% to 99% vs the sample size between 30 and 45, when the ORR $>5\%$  with a type I error rate of 1.25% [28]. Success for this hypothesis requires at least 6 responses out of 30~39 subjects with PD-L1 strongly positive, and at least 7 responses out of 40~45 subjects with PD-L1 strongly positive. The power may increase or decrease depending on the actual number of PD-L1 strong positive subjects who are enrolled in the study ([Figure 3](#)).

[figure not shown]

Figure 3 Power Curve vs Sample Size of PD-L1 Strong Positive Subjects

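### Does the primary ORR definition leave open whether a response must be confirmed by a second scan?

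*Combined protocol and SAP*

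**What the plan says.** The statistical analysis plan is Section 8 of the protocol, and "No separate Statistical Analysis Plan (SAP) will be issued for this study".

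- **Endpoint.** Section 8.2.3.1 counts subjects with "complete response (CR) or partial response (PR) using RECIST 1.1 criteria at any time during the study", judged by independent radiology review.
- **Confirmation.** Section 7.1.2.6.2 says that, per RECIST 1.1, "response should be confirmed by a repeat radiographic assessment not less than 4 weeks from the date the response was first documented". It allows the confirming scan at 4 weeks or at the next scheduled visit, and gives an example of a Week 9 response confirmed at Week 13.
- **Who applies the criteria.** Section 7.1.2.6.3 has the central imaging vendor apply RECIST 1.1 as the primary measure of response. Appendix 12.7 adopts RECIST 1.1 for response assessment.
- **Timing.** Section 8.2.5.1: "The primary analysis for each hypothesis will be conducted after all subjects have at least 6 months of follow-up".
- **Success rule.** Section 8.2.7, for all subjects: "Success for this hypothesis requires at least 14/135 responses". For PD-L1 strong positive subjects it requires 6 responses if there are 30 to 39 subjects and 7 if there are 40 to 45.
- **Recycled alpha.** Section 8.2.6: if the strong-positive and PD-L1 positive hypotheses are both rejected, "the primary efficacy hypothesis for all subjects will be tested at 2.5" percent.

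**The concern.** In a single-arm trial tested against a fixed rate, the rule for who counts as a responder is the core of the success criterion. Section 8 never applies the word confirmed to ORR. Elsewhere the protocol does use it: the retreatment criteria in Section 7.1.5.2.1 require an "investigator-determined confirmed CR according to RECIST 1.1". Section 4.1.3 reports the earlier trial's result as "showing an overall response rate (confirmed and unconfirmed) of 19.6" percent, so the authors knew that the two counts differ.

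Read literally, a single scan showing PR could be enough. The sponsor's team is blinded to PD-L1 results but not to response, and there is no later SAP to settle the point. If the rule were chosen once the central reads were known, a result near the boundary could be moved from failure to success.

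Timing adds a second question. A late responder may not have had the confirming scan when the primary analysis is run, and no sentence says how that subject counts.

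**Working it through.** **1. The plan's thresholds.** Inputs are the 5% null rate (Section 8.2.5.1), one-sided 1.25% for each primary test (Section 8.2.6), and the sample sizes in Section 8.2.7. The threshold is the smallest r with P(X ≥ r | n, 0.05) ≤ 0.0125.

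| n | r | P(X ≥ r) | P(X ≥ r − 1) |
|---|---|---|---|
| 135 | 14 | 0.0079 | 0.0181 |
| 36 | 6 | 0.0083 | 0.0324 |
| 45 | 7 | 0.00665 | 0.0239 |

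The threshold is 6 for every n from 30 to 39 and 7 for every n from 40 to 45, as the plan states. These values depend only on n, the 5% and the 1.25%, so they hold whether or not responses must be confirmed. One response at the boundary does decide each test at 1.25%. With recycled alpha, 13 of 135 would pass, since 0.0181 < 0.025.

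**2. Which count the text gives.** Section 8.2.3.1 sets the standard (RECIST 1.1), and Section 7.1.2.6.2 says what the protocol takes that standard to require (confirmation at 4 weeks or later). Together they give confirmed CR or PR. The words about any time during the study say when a response may occur, not how many scans establish it. The retreatment wording concerns an investigator's decision, and it fits equally well with RECIST 1.1 carrying confirmation.

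**3. How often the counts would lead to different decisions.** Confirmed responders are a subset of all responders. If a share s of responses is confirmed, independently between subjects, then

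P(any ≥ 14 and confirmed < 14) = P(X ≥ 14 | 135, p) − P(X ≥ 14 | 135, p·s).

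The documents give no s, so 90% and 80% are assumptions. The planning alternative is not visible. A rate of p = 13% reproduces the stated 85% power (0.851), and treating it as an any-response rate is a further assumption. The only any-response rate in the documents for all subjects with this disease is 19.6% (11 of 56, Section 4.1.3).

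| p | s | p·s | P at p | P at p·s | Difference |
|---|---|---|---|---|---|
| 0.196 | 0.9 | 0.1764 | 0.9987 | 0.9932 | 0.0055 (about 0.6%) |
| 0.196 | 0.8 | 0.1568 | 0.9987 | 0.9708 | 0.0279 (2.8%) |
| 0.13 | 0.9 | 0.117 | 0.851 | 0.723 | 0.128 (12.8%) |
| 0.13 | 0.8 | 0.104 | 0.851 | 0.546 | 0.305 (30.5%) |

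**4. Direction of error.** If 5% is a confirmed-response rate, the confirmed count has a false-positive probability of 0.79% for all subjects. If 5% includes unconfirmed responses, the confirmed rate under the null is below 5% and that probability is lower still. Inflation arises only if one-scan responses are counted against a confirmed null. If they added an assumed 1 or 2 percentage points, P(X ≥ 14 | 135) would be 0.0326 at 6% and 0.0910 at 7%.

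**5. Responses pending at the analysis.** Scans fall at weeks 9, 15, 21 and 27. A response first seen at week 9 or 15 can be confirmed by week 15 or 21. One first seen at week 21 can be confirmed from week 21 + 4 = 25, or at the week-27 visit, which may take place at week 26 under the ±7-day window. Six months is about 26 weeks, and it is a minimum for the last subjects, not a fixed cut-off for everyone. The exposed group is therefore late-enrolled subjects who first respond at week 21 or later and have not yet been rescanned.

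**The case for a change.** The strongest case is that a success rule should not rest on inference. The confirmation sentence sits in an imaging section, is worded as something that should happen, and does not say that an unconfirmed response is a non-response in the analysis. Response duration starts at first response with no condition attached. The commitment in Section 8.0 to amend the protocol for changes to the primary hypotheses or methods is tied to the time before PD-L1 status is known, not to the time before response is known. The missing-data rule covers subjects without response data, and a subject with one scan showing PR has some. Follow-up scans off treatment may be up to 12 weeks apart in the first year, which could delay confirmation further.

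Part of this stands. Section 8 does not repeat the requirement, and no sentence covers a response still pending at the analysis. But dating duration from first response is compatible with a confirmed responder set. A pending response has not met the confirmation requirement, so under the confirmed reading it does not count. That can lower the numerator but cannot raise it. To use the one-scan count, an analyst would have to set aside the protocol's own account of the criteria that the endpoint invokes.

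The 13% scenario cannot be dismissed either. The protocol requires resistance to both platinum and cetuximab and does not describe the earlier cohort in those terms, so 19.6% may be optimistic here. That affects how much the choice of count would matter, not which count the text gives.

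**Conclusion.** No change follows. Read as a whole, the protocol makes the primary endpoint confirmed CR or PR by RECIST 1.1 under independent review. What is missing is a repeated word in Section 8 and a sentence on pending responses, and both are gaps that an analyst working from the document would fill soundly and on the conservative side. The thresholds of 14 of 135, 6 of 30 to 39 and 7 of 40 to 45 reproduce and are unaffected.

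The consequence of the choice is uncertain. With 80% to 90% of responses confirmed, the two counts would give different all-subjects decisions at 1.25% with probability 0.6% to 2.8% at 19.6%, and 12.8% to 30.5% at an any-response rate of 13%. The confirmation shares are assumed and the 13% is back-solved from the stated power. If 13% is instead a confirmed rate, the stated 85% power already applies to the confirmed count. The planning alternative is blacked out in the public text, so a missing label on it cannot be held against the plan.
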